## **12. ASSESSMENT OF SAFETY**

### **12.1. Safety Parameters**

Safety will be assessed through routine medical monitoring of AEs/SAEs and laboratory parameters as described in the Schedule of Activities (Table 2). Specific assessments are discussed in detail below.

#### **12.1.1. Demographic/Medical History**

Medical history and medication history (up to 30 days prior to Screening), demographics, and known co-morbidities will be collected from all subjects at Screening. The number of days between onset of COVID-19 symptoms and initiation of treatment will be recorded in all subjects.

Investigators will have the discretion to record abnormal test findings on the medical history case report form (CRF) whenever, in their judgment, the test abnormality occurred prior to the informed consent signature.

#### **12.1.2. Vital Signs**

Vital signs will be recorded at Screening, Day 1, and throughout the study period as specified in the Schedule of Activities (Table 2).

#### **12.1.3. Physical Examination**

A physical examination of each subject will be conducted at Screening and at the Discharge/UNS visit. Height and weight will be collected at Screening only.

#### **12.1.4. Electrocardiogram, and Chest X-ray or CT Scan**

An ECG will be obtained at Screening and at the Discharge/UNS visit. A chest x-ray or chest CT scan will be obtained at Screening. The chest x-ray will be repeated at the Discharge visit. Additional chest x-rays or CT scans may be performed from Screening through Day 29 at the discretion of the Investigator and these results must be recorded.

#### **12.1.5. Laboratory Assessments**

All safety laboratory parameters in the study will be conducted at Screening (as per Table 2) with additional post-dose timepoints noted in Table 4.

Subjects who are discharged should complete the Discharge/UNS visit (the study day assessments are not required). If a subject is discharged and the Investigator judges that it is not safe for the subject to return to the site, or the subject is not willing to return to the site, the visits that occur thereafter may be done by telemedicine and lab tests and other procedures will not be performed. Additional laboratory assessment may be performed from Screening through Day 29 at the discretion of the Investigator and these results must be recorded.

**Table 4: Schedule of Laboratory Assessments**

Activity / Parameter	Collection Detail	Collection Timepoints
CENTRAL LABORATORY		
Respiratory Panel	A/H3N2, A/H1N1pdm09, A/H7N9, A/H5N1, A, not typed, B, or other (specify); coronavirus – novel CoV, MERS CoV, other CoV (specify); RSV; adenovirus; bacteria; other infectious respiratory diagnosis (specify); clinical pneumonia	Screening
██████████	██████████	████████████████████ ████████████████████ ████████████████████
██████████ ██████████	████████████████████ ████████████████████ ████████████████████ ████████████████████ ████████████████████ ████████████████████	████████████████████ ████████████████████ ████████████████████
Anti-mavrilimumab antibody		Screening and the Discharge/UNS visit
Pharmacokinetic sample		Day 1 (before infusion and when infusion is complete), Days 3±1, 7±1, 15±2, 29+4 and at the Discharge/UNS visit
LOCAL LABORATORY		
Pregnancy test (women of child-bearing potential)	Urine or serum βhCG	Screening and at the Discharge/UNS visit; Day 90+14 is optional
██████████ ██████████		████████████████████ ████████████████████ ████████████████████
Hematology	Complete blood count + differential	Screening (up to 7 days prior to randomization), Days 3±1, 15±2, 29+4 and at the Discharge/UNS visit; Days 60+14 and 90+14 are optional
Coagulation	PT, PTT, and INR	
Chemistry	electrolytes, blood urea nitrogen, glucose and CR	
Liver Profile	AST, ALT, Alb, AlkP, Tbili, Dbili	

Activity / Parameter	Collection Detail	Collection Timepoints
Lipid Panel	Cholesterol, total; high-density lipoprotein (HDL) cholesterol; low-density lipoprotein (LDL) cholesterol (calculation); triglycerides; very low-density lipoprotein (VLDL) cholesterol (calculation)	Screening (up to 7 days prior to randomization) and at the Discharge/UNS visit
Urinalysis		Screening (up to 7 days prior to randomization) and Discharge/UNS visit; Day 29+4, Days 60+14 and 90+14 are optional
Tuberculosis		Optional at Screening - at Investigator's discretion South Africa only: TB testing required for all subjects at Screening
SARS-CoV-2	COVID-19	Screening* Days 1, 2, 3, 4, 5, 6, 7, 8, 15 ±2, 22 ±2, 29 +4 and Discharge/UNS are optional

Screening = up to 3 days prior to randomization

\*For SARS-CoV-2 testing (COVID-19), a positive test within 14 days of randomization is required. Sites that are unable to perform SARS-CoV-2 locally (at the clinical site or from another institution) may use Central Laboratory testing.

The full Schedule of Activities is presented in [Table 2](#).

#### 12.1.5.1. Pregnancy Screen

All pre-menopausal women who are not surgically sterile will have a urine or serum pregnancy test performed at Screening. Pregnancy testing is not required for post-menopausal women. For female subjects of childbearing potential who are discharged and return to the site later, a pregnancy test must be repeated at the last visit the subject completes on the study.

#### 12.1.6. Sequential Organ Failure Assessment (SOFA) and Quick SOFA

Sequential Organ Failure Assessment (SOFA) and Quick SOFA (qSOFA) are clinical assessments to identify subjects with worsening health status in ICU and non-ICU environments, respectively. Cohort 1 (non-ventilated) subjects will be assessed using qSOFA at Screening. Cohort 2 (ventilated) subjects will be assessed using SOFA at Screening and at Day 8.

If a subject experiences a 1-point worsening in NIAID, it is recommended to re-assess qSOFA (Cohort 1) or SOFA (Cohort 2) at the time of worsening or as per standard of care during hospitalization.

Additional SOFA/qSOFA assessments may be performed from Screening through Day 29 at the discretion of the Investigator and these results must also be recorded.

## **12.2. Adverse and Serious Adverse Events**

### **12.2.1. Definition of Adverse Events**

#### **12.2.1.1. Adverse Event (AE)**

An AE is any untoward medical occurrence (eg, any unfavorable and unintended sign [including abnormal laboratory findings], symptom or disease) in a clinical investigation subject after providing written informed consent for participation in the study. Therefore, an AE may or may not be temporally or causally associated with the use of a medicinal (investigational) product.

Abnormal laboratory values or test results constitute AEs only if they fulfill at least one of the following criteria:

- they induce clinical signs or symptoms
- they are considered clinically significant
- they require therapy

Clinically significant abnormal laboratory values or test results must be identified through a review of values outside of normal ranges/clinically notable ranges, significant changes from baseline or the previous visit, or values, which are considered non-typical in subjects with the underlying disease.

#### **12.2.1.2. Adverse Drug Reaction**

An adverse drug reaction is defined as, “A response to a medicinal product which is noxious and unintended [DIR 2001/83/EC Art 1(11)]. Response in this context means that a causal relationship between a medicinal product and an AE is at least a reasonable possibility” (see Annex IV, ICH-E2A Guideline).

Information about adverse drug reactions for the investigational drug can be found in the Investigator’s Brochure.

#### **12.2.1.3. Adverse Events of Special Interest**

An AE of special interest (AESI) is one of scientific and medical interest specific to understanding of the investigational product and requires close monitoring and communication by the Investigator to the Sponsor within 24 hours of knowledge of the event, regardless of seriousness criteria. The rapid reporting of AESIs allows ongoing analysis of these events in order to characterize and understand them in association with the use of this investigational product.

#### **Hepatic Function Abnormality / Drug-induced Liver Injury**

Drug-induced liver injury (DILI) is considered an AESI and should be reported within 24 hours of knowledge of the event. In subjects with normal liver function at baseline, DILI is defined as an increase in ALT or AST to greater than  $3 \times \text{ULN}$  with concurrent increase in bilirubin to greater than  $2 \times \text{ULN}$ , without another explanation. In subjects with abnormal ALT and/or AST and/or bilirubin at baseline, it is operationally defined as a doubling of ALT or AST and bilirubin, without another explanation. Concurrent findings are those that derive from a single

blood draw or from separate blood draws taken within 8 days of each other. In the event of hepatic function abnormality where the etiology is unknown, timely follow-up investigations and inquiries should be initiated by the investigational site, based on medical judgment, to make an informed decision regarding the etiology of the event.

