8. If subject is receiving or has received hydroxychloroquine within 3 months prior to randomization, a corrected QT interval by Fridericia's method (QTcF) on Screening electrocardiogram (ECG) of  $\geq 500$ ms is exclusionary. If subject has a pacemaker, this criterion does not apply.

9. *[Original Criteria Deleted]*

10. Enrolled in another investigational study of a medical intervention within 30 days prior to randomization. Participation in open label trials involving investigational treatments for COVID-19 may be allowed upon approval by the Sponsor.

11. Known hypersensitivity to mavrilimumab or any of its excipients

12. In the opinion of the Investigator, unable to comply with the requirements to participate in the study

13. *[Original Criteria Deleted]*

14. *[Original Criteria Deleted]*

15. At Screening blood tests, any of the following:

- Aspartate transaminase (AST)  $> 10 \times$  upper limit of normal (ULN)
- Alanine transaminase (ALT)  $> 10 \times$  ULN
- Hemoglobin  $< 7.5$  g/dL
- Neutrophils  $< 1,500/\text{mm}^3$
- Absolute platelet count  $< 50,000/\text{mm}^3$
- Creatinine clearance  $< 30$  mL/min (by Cockcroft-Gault formula) (Cockcroft DW, 1976)

16. Life expectancy less than 48 hours, in the opinion of the Investigator

17. Known human immunodeficiency virus infection (regardless of immunological status), known hepatitis B virus surface antigen positivity and/or anti-hepatitis C virus positivity

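### A subject who enters with high liver enzymes can reach the protocol's own 3 x ULN / 2 x ULN levels after dosing and still not be a DILI event of special interest

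*Combined protocol and SAP*

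**What the plan says.** Protocol section 12.2.1.3, under Hepatic Function Abnormality / Drug-induced Liver Injury, has two branches.

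- Normal baseline: "In subjects with normal liver function at baseline, DILI is defined as an increase in ALT or AST to greater than" 3 x ULN, "with concurrent increase in bilirubin to greater than" 2 x ULN, without another explanation.
- Abnormal baseline: the group is introduced by the words "In subjects with abnormal ALT and/or AST and/or bilirubin at baseline", so one abnormal test is enough to place a subject here. The criterion for this group names no multiple of the ULN: "it is operationally defined as a doubling of ALT or AST and bilirubin, without another explanation".

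Findings count as concurrent if they come from a single "blood draw or from separate blood draws taken within 8 days of each other". On reporting, "Drug-induced liver injury (DILI) is considered an AESI and should be reported within 24 hours of knowledge of the event".

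Exclusion criterion 15 in section 7.2 ("At Screening blood tests, any of the following") removes subjects with AST or ALT above 10 x ULN. It sets no limit for bilirubin.

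The Phase 3 SAP tabulates treatment-emergent AESIs by system organ class and preferred term (5.8.1). For the liver profile it plans descriptive statistics over time and by-subject listings (5.8.2). At the first Cohort 1 database lock, laboratory data are analysed at baseline only and shift tables are omitted (4.6 and section 6). The visible text of the protocol and both SAPs contains no other post-baseline liver threshold.

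**The concern.** One abnormal test moves the whole subject from a rule tied to the ULN to a rule tied only to the subject's own baseline. The higher the entry value, the larger the absolute rise that doubling requires. Subjects with the worst entry enzymes are thus the ones for whom the AESI definition is hardest to meet, even when bilirubin has newly risen from normal to well above the level that counts in other subjects.

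At stake are the 24-hour report to the sponsor, which applies whether or not the event is serious, and the completeness of the AESI table. No planned output would pick such subjects out. By-visit means can hide individual cases, a full by-subject listing does not flag them, and the first lock summarises no post-baseline laboratory data.

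**Working it through.** The plan gives no figure to reproduce here. The check applies both branches to illustrative subjects who could enter the trial. All values are multiples of the ULN. The laboratory values are assumptions chosen to test the logic, not trial data.

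**Inputs**
- Normal-baseline rule (12.2.1.3): (ALT > 3 or AST > 3) and bilirubin > 2.
- Abnormal-baseline rule (12.2.1.3): (ALT or AST at least 2 x baseline) and bilirubin at least 2 x baseline.
- Highest ALT or AST at entry (7.2, criterion 15): 10.

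**Where the rules cross.** For ALT or AST, 2 x baseline = 3 at a baseline of 1.5; above that, doubling asks for more than 3 x ULN. For bilirubin, 2 x baseline = 2 at a baseline of 1.0. At the entry limit, doubling requires 2 x 10 = 20 x ULN for ALT or AST.

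**High entry enzymes, bilirubin not above the ULN at entry**

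| Subject | ALT | AST | Bilirubin | Doubling met? | 3 x / 2 x levels reached? |
|---|---|---|---|---|---|
| A | 6 to 11 (11/6 = 1.83) | not doubled | 0.8 to 4.0 (5.0-fold) | No | Yes |
| B | 6 to 11.5 (1.92) | 5 to 9.5 (1.90) | 0.8 to 4.0 (5.0-fold) | No | Yes |
| C | 4 to 7.9 (1.98) | 4 to 7.9 (1.98) | 0.5 to 3.0 (6-fold) | No | Yes |
| D | 10 to 19.9 (1.99) | 10 to 19.9 (1.99) | 1.0 to 6.0 (6-fold) | No | Yes |

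In each row bilirubin more than doubles and passes 2 x ULN. The case is lost only because neither aminotransferase doubled from an already high value.

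**Sensitivity to wording.** The phrase joining ALT, AST and bilirubin has no brackets. Read instead as ALT doubled, or else AST and bilirubin both doubled, rows A to D are still not flagged, because neither ALT nor AST doubles.

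A second pattern does depend on that reading. With ALT 0.5 to 15, AST 0.5 to 12 and bilirubin 1.5 to 2.9 (2.9/1.5 = 1.93), the first reading does not flag the subject despite a 30-fold ALT rise; the second does. The grouping therefore needs to be stated as well.

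**The case against.** The strongest reply is that a baseline-relative rule for abnormal entry values is reasonable and is meant to differ from a ULN rule. Subject A was already at twice the 3 x ULN limit before dosing (6/3 = 2), so the enzyme part of the ULN rule says little about the drug. The case is also not invisible. Section 12.2.1.1 asks for review of significant changes from baseline, 12.2.1.3 asks for follow-up of unexplained hepatic abnormality, and a medically significant event is an SAE with its own 24-hour report (12.2.1.4, 12.5). Liver values are summarised and listed, and the DMC sees unblinded safety data. All of this stands. It limits the loss to the automatic AESI trigger and possibly the AESI table entry. It does not supply an output that identifies these subjects.

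Three stronger readings are tempting but not supported.

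- A reader might infer that doubling fills the AESI table with normal-range changes, such as ALT 0.4 to 0.8 and bilirubin 0.4 to 0.8 x ULN in a subject whose only abnormal test is AST. An AESI must first be an AE, and section 12.2.1.1 counts laboratory values as AEs only if they cause symptoms, are clinically significant or need therapy. No visible SAP text applies the doubling rule to raw laboratory data.
- A reader might call the two branches contradictory. They cover separate groups, so they do not give two answers for one subject.
- A reader might conclude that the hepatic comparison between arms is unreliable. The definition is the same in every arm of a double-blind trial, no formal safety testing is planned (13.2.5), and no misclassification rate can be derived.

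**Conclusion.** The point holds as a gap in the AESI trigger. Because the abnormal-baseline branch has no ULN anchor and entry allows ALT and AST up to 10 x ULN, an eligible subject can reach the protocol's 3 x ULN / 2 x ULN levels after dosing, with bilirubin newly raised, and not be a DILI AESI. At the entry limit the enzyme part is met only at 20 x ULN. The qualifier about another explanation appears in both branches and cannot recover a case that fails the numerical test.

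This rests on reading abnormal as above the ULN and doubling as at least twice baseline, and in subject A on AST not doubling. How many subjects are affected cannot be computed, since the documents do not give the share with abnormal baseline tests. The remedy is a cheap improvement; the case does not show that the safety analysis is invalid.

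**What to change.** Add to section 5.8.2 of the Phase 3 SAP a programmed listing, with a count by arm, of every subject with post-baseline ALT or AST above 3 x ULN and concurrent bilirubin above 2 x ULN. Use the protocol's 8-day window, include all subjects whatever their baseline, show the baseline values, and provide the output to the sponsor and the DMC. It uses the protocol's own thresholds and data already collected. Because only baseline laboratory data are cleaned for the first lock, it falls due at the second lock unless post-baseline laboratory cleaning is brought forward.

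Separately, ask the sponsor to reconcile the two branches of section 12.2.1.3 with the entry limits in section 7.2, and to state how ALT, AST and bilirubin are grouped in the doubling rule. This review does not set the threshold. Keeping doubling only for tests that were abnormal at entry would not close the gap: subject A's ALT was abnormal, and 11/6 is still below 2.

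The cost is a short SAP addition, one program and a protocol clarification. The downside is a few extra cases to review, including subjects who entered with ALT or AST already above 3 x ULN; the baseline values in the listing make these easy to recognise.

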### Acute and Delayed Hypersensitivity Reactions

Biologic therapies are known to be associated with an increased risk of immediate and delayed hypersensitivity reactions as well as anaphylaxis. Anaphylaxis is defined below in Table 5 using Sampson's criteria (Sampson HA, 2006). Anaphylaxis and severe hypersensitivity reactions are required to be reported within 24 hours of knowledge of the event.

**Table 5: Clinical Criteria for Diagnosing Anaphylaxis**

Anaphylaxis is highly likely when any one of the following 3 criteria are fulfilled:	
1.	Acute onset of an illness (minutes to several hours) with involvement of the skin, mucosal tissue, or both (eg, generalized hives, pruritus or flushing, swollen lips-tongue-uvula)  AND AT LEAST ONE OF THE FOLLOWING: 

a. Respiratory compromise (eg, dyspnea, wheeze-bronchospasm, stridor, reduced PEF, hypoxemia)

b. Reduced BP or associated symptoms of end-organ dysfunction (eg, hypotonia [collapse], syncope, incontinence)

2.	Two or more of the following that occur rapidly after exposure to a likely allergen for that patient (minutes to several hours): 

a. Involvement of the skin-mucosal tissue (eg, generalized hives, itch-flush, swollen lips-tongue-uvula)

b. Respiratory compromise (eg, dyspnea, wheeze-bronchospasm, stridor, reduced PEF, hypoxemia)

c. Reduced BP or associated symptoms (eg, hypotonia [collapse], syncope, incontinence)

d. Persistent gastrointestinal symptoms (eg, crampy abdominal pain, vomiting)

3.	Reduced BP after exposure to known allergen for that patient (minutes to several hours): 

a. Infants and children: low systolic BP (age specific) or greater than 30% decrease in systolic BP*

b. Adults: systolic BP of less than 90 mm Hg or greater than 30% decrease from that person's baseline

PEF, Peak expiratory flow; BP, blood pressure.

\*Low systolic blood pressure for children is defined as less than 70 mm Hg from 1 month to 1 year, less than (70 mm Hg 1 + [2 × age]) from 1 to 10 years, and less than 90 mm Hg from 11 to 17 years.

## Neutropenia

AEs of neutropenia of special interest to the Sponsor (defined as an ANC  $< 1.0 \times 10^9$  cells/L) will be considered an AESI and should be reported within 24 hours of knowledge of the event.

## Serious Infection

Infections meeting SAE criteria (eg, required hospitalization) or infections with a severity grade of “severe” that require treatment with IV therapy (antibiotics, antiviral, or antifungal) and opportunistic infections will be considered AESI and should be reported within 24 hours of knowledge of the event.

Every effort should be made to identify the causative pathogen through prompt and appropriate investigation by the Investigator or reporting physician.

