**The efficacy and safety results from the KPL-301-C203, Phase 2 Cohort 1 subjects**, support use of both doses of mavrilimumab in the ongoing Phase 3 study. While generally there are no apparent differences between the two mavrilimumab arms for efficacy and safety, given the small number of primary events of ventilation and/or death analyzed to date, there are some differences between the two doses in mortality (10 mg/kg is numerically efficacious) or ventilation-free survival (6 mg/kg is numerically more efficacious). Overall, both the 10 mg/kg and the 6 mg/kg appear well-tolerated with no new identified safety risks in the COVID-19 study population. In fact, serious infections (e.g., septic shock, sepsis) were substantially lower in both mavrilimumab dose arms compared to placebo, and thrombosis events were only reported in the placebo arm. There were no serious adverse events related to mavrilimumab, no dose-related adverse events and no infusion reactions.

**Important potential risks for mavrilimumab** will continue to be monitored. These include severe hypersensitivity reactions, immune complex disease, serious infections (viral, bacterial, and opportunistic infections), malignancy, vaccine interactions, pulmonary alveolar proteinosis, reproductive toxicity and granulocytic effects, including neutropenia. Of note, there is no biological rationale for several of these potential risks in the setting of a single dose administration. More importantly, none of these potential risks have been identified in the RA development program through Phase 2b with approximately 900 subject-years of exposure. See Investigator's Brochure for additional details.

This clinical study was designed and shall be implemented, executed, and reported in accordance with the ICH Tripartite Guidelines for Good Clinical Practice, with applicable local regulations, US Code of Federal Regulations (CFR) 21, and with the ethical principles laid down in the Declaration of Helsinki.

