### 12.2.1.4. Serious Adverse Event (SAE)

An SAE is defined as any AE (appearance of [or worsening of any pre-existing] undesirable sign(s), symptom(s) or medical condition(s)) which meets any one of the following criteria:

- results in death
- is life-threatening
  - Life-threatening in the context of a SAE refers to a reaction in which the subject was at risk of death at the time of the reaction; it does not refer to a reaction that hypothetically might have caused death if it were more severe (please refer to the ICH-E2D Guidelines)
- results in persistent or significant disability/incapacity
- constitutes a congenital anomaly/birth defect
- requires inpatient hospitalization or prolongation of existing hospitalization, unless hospitalization is for:
  - routine treatment or monitoring of the studied indication, not associated with any deterioration in condition (coronary heart disease, cerebrovascular disease or peripheral vascular disease)

- elective or pre-planned treatment for a pre-existing condition that is unrelated to the indication under study and has not worsened since signing the informed consent
- social reasons and respite care in the absence of any deterioration in the subject's general condition
- treatment on an emergency outpatient basis for an event not fulfilling any of the definitions of a SAE given above and not resulting in hospital admission
- is medically significant, eg, defined as an event that jeopardizes the subject or may require medical or surgical intervention to prevent one of the outcomes listed above.

Medical and scientific judgment should be exercised in deciding whether other situations should be considered serious reactions, such as important medical events that might not be immediately life threatening or result in death or hospitalization but might jeopardize the subject or might require intervention to prevent one of the other outcomes listed above. Such events should be considered as “medically significant”. Examples of such events are intensive treatment in an emergency room or at home for allergic bronchospasm, blood dyscrasias or convulsions that do not result in hospitalization or development of dependency or abuse.

All malignant neoplasms will be assessed as serious under “medically significant” if other seriousness criteria are not met.

Any suspected transmission via a medicinal product of an infectious agent is also considered a serious adverse reaction.

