## Exceptions to SAE Reporting

Events that are captured as protocol-mandated clinical outcome measures (ie, part of the 8-point NIAID scale) should not be reported as SAEs. This would include initiation of invasive mechanical ventilation and/or ECMO, non-invasive ventilation or high-flow oxygen, and supplemental oxygen. In addition, procedures associated with these clinical outcome measures (eg, intubation or tracheostomy) should not be reported as SAEs. Events that in the judgment of the investigator are clearly a part of the natural history of severe COVID-19 pneumonia with hyper-inflammation should not be reported as SAEs (eg, fever, elevated CRP). All deaths, serious infections and severe granulocytopenia and neutropenia should be reported as SAEs. Per the Investigator Brochure, pneumonia is the only event that is included in the Reference Safety Information (RSI) and would be considered expected or listed. Any other serious related adverse drug reactions would be considered unexpected and would require expedited reporting.

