#### 5.8.1. Adverse Events

An adverse event (AE) is any untoward medical occurrence in a subject or clinical investigation subject administered a pharmaceutical product. An AE does not necessarily have a causal relationship with this treatment. An AE will be defined as treatment-related if its relationship to the study drug is reported as Possibly Related or Definitely Related by Investigator.

An AE is considered treatment-emergent adverse event (TEAE) if the AE begins on/after and within 90 days of the study drug administration. If the date of AE onset is missing or coincides with the date of the study drug administration and AE time is not captured, AE will be considered treatment emergent.

All AEs will be coded using MedDRA version 23.0. A subject experiencing multiple AEs under the same preferred term (PT) or same system organ class (SOC) will be counted only once for that PT or SOC by maximum severity. If a subject experience the same AE more than once with more than one causal relationship to study drug, the strongest causal relationship to study drug will be given precedence. Any missing severity, causality, or outcome will not be imputed and classified as 'Missing'. Detailed imputation rules for missing AE dates are in Section 8.1.1.

An adverse event of special interest (AESI) is one of scientific and medical interest specific to understanding of the Investigational Product and requires close monitoring and rapid communication by the investigator to the sponsor. An AESI may be serious or non-serious.

The number of subjects with at least one TEAE will be tabulated. The following tables summarize incidences of various aspects of TEAEs, treatment-emergent serious AEs (TESAEs), and treatment-emergent AESIs (TEAESIs):

- Overview of TEAEs (summary of all the subsequent items)
- TEAEs by SOC and PT
- TEAEs by PT
- TEAEs by maximum severity (mild, moderate, or severe)
- Drug related TEAEs (related or not related) by SOC and PT
- TESAEs by SOC and PT
- Drug related TESAEs by SOC and PT
- TESAEs by PT
- TEAESIs by SOC and PT
- TEAEs leading to dose interruption by SOC and PT
- TEAEs leading to death by SOC and PT

All information pertaining to adverse events will be listed by subject, detailing verbatim term given by the investigator, preferred term, system organ class, start date, stop date, severity, outcome, action taken and drug relatedness.

Separate listings will be created for Serious TEAEs, and TEAESI, and death.

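### The serious-infection AESI does not exclude index COVID-19, so its pooled count can fall through efficacy and partly mask an excess of secondary infections

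*Combined protocol and SAP*

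**What the plan says.** - **Protocol 12.2.1.3, Serious Infection.** The definition has two limbs, the first resting on seriousness and the second on the severe grade: "Infections meeting SAE criteria (eg, required hospitalization) or infections with a severity grade of". The second limb is limited to infections "that require treatment with IV therapy (antibiotics, antiviral, or antifungal) and opportunistic infections will be considered AESI". SARS-CoV-2 is not carved out. The opening of 12.2.1.3 makes AESIs reportable "regardless of seriousness criteria".
- **Protocol 12.2.1.4.** The SAE definition covers "appearance of [or worsening of any pre-existing] undesirable sign(s), symptom(s) or medical condition(s", and a fatal result is one of the seriousness criteria.
- **Protocol 12.5, Exceptions to SAE Reporting.** Outcomes captured on the NIAID scale are not SAEs: "This would include initiation of invasive mechanical ventilation and/or ECMO", as well as lesser oxygen support. Nor are events that the investigator judges clearly part of the natural history of the disease. The same paragraph then says: "All deaths, serious infections and severe granulocytopenia and neutropenia should be reported as SAEs".
- **Protocol 12.4.** Conditions present at consent go to medical history. Later worsening or death from such a condition is not addressed there.
- **Phase 3 SAP 5.8.1.** AESIs appear in an overview and as "TEAESIs by SOC and PT". Similar tables cover serious and fatal events, and there are subject listings. No table is by AESI category, and none separates index COVID-19 from other infections.
- **Protocol 13.2.5.** Safety is summarised descriptively, without formal analysis.
- **Protocol Section 4, dose rationale.** Serious infection (viral, bacterial and opportunistic) is a listed potential risk. For Phase 2 Cohort 1 the protocol reports that "serious infections (e.g., septic shock, sepsis) were substantially lower in both mavrilimumab dose arms compared to placebo".

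**The concern.** Every subject already has the infection that the AESI fails to exclude, and death from it is a failure on the Cohort 1 primary endpoint. If mavrilimumab prevents COVID-19 deaths, the count of subjects with an infection AESI falls for that reason, whatever the drug does to bacterial, fungal or other secondary infections. For an immunomodulator, the second question is the safety question. A pooled count that is level or lower on drug could be read as reassurance while secondary infections are more frequent. The protocol has already drawn a favourable comparative statement about serious infections, so the Phase 3 figure is likely to be read in the same way.

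**Working it through.** **1. Which index-disease events meet the AESI?**

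| Event | 12.2.1.3 and 12.2.1.4 | 12.5 | Reading |
|---|---|---|---|
| COVID-19 as present at consent | Not a new event | Not addressed; 12.4 sends it to medical history | Not an AESI |
| Fatal COVID-19 pneumonia | Infection that worsened, with fatal result | All deaths are SAEs | Meets the AESI |
| Start of ventilation or ECMO | Could be worsening of an infection | Not an SAE | Unclear |
| Severe COVID-19 given an IV antiviral | Fits the second limb, which does not need seriousness | Natural-history exception may apply, but only to SAE reporting | Unclear |

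**2. The plan's own figure.** Protocol 13.3.2 assumes success of 74.4% (placebo) and 87.5% (active) with 200 per arm, two-sided alpha 0.05, and at least 90% power. Power = Φ[(d − 1.96·SE₀)/SE₁], with d = 0.131.
- SE₀ = √(2 × 0.8095 × 0.1905/200) = 0.0393
- SE₁ = √((0.744 × 0.256 + 0.875 × 0.125)/200) = 0.0387
- Power = 91.9%, so the stated figure reproduces. The implied failure rates are 25.6% and 12.5%.

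**3. Dilution in the pooled count.** Let f be the share of primary-endpoint failures also recorded as an index-infection AESI, and s the rate of serious secondary infection. Assume f is the same in both arms and the two kinds of event are independent. Then

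P(any infection AESI) = 1 − (1 − f × failure rate)(1 − s).

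Neither f nor s is in the documents. Take s = 8% on placebo and 16% on active, a true ratio of 2.00:

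| f | Placebo | Active | Ratio |
|---|---|---|---|
| 0 | 8.0% | 16.0% | 2.00 |
| 0.25 | 13.9% | 18.6% | 1.34 |
| 0.5 | 19.8% | 21.3% | 1.07 |
| 0.75 | 25.7% | 23.9% | 0.93 |
| 1 | 31.6% | 26.5% | 0.84 |

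For f = 0.5: 1 − (1 − 0.128)(0.92) = 0.198 and 1 − (1 − 0.0625)(0.84) = 0.213. As a gauge of signal only, a two-sided 0.05 comparison at 200 per arm has about 69% power at f = 0, 25% at f = 0.25 and 6% at f = 0.5.

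Ventilation is named in the 12.5 exceptions. Values of f near 1 would therefore need ventilated survivors to be recorded as infection AESIs, and they are outer bounds.

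**4. Excess that would look like balance.** Setting the pooled rates equal gives s₁ = 1 − (1 − 0.256f)(1 − s₀)/(1 − 0.125f). Ratios s₁/s₀ at placebo rates of 5%, 8% and 10%:
- f = 0.25: 1.64, 1.39, 1.30
- f = 0.5: 2.33, 1.80, 1.63
- f = 1: 3.84, 2.72, 2.35

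**5. Precision of the separated contrast.** Phase 3 SAP 1.2 gives 581 subjects, about 194 per arm. For assumed rates of 5% and 8%, the 95% half-width is 1.96 × √(0.05 × 0.95/194 + 0.08 × 0.92/194) = 4.9 points. The separate count would be imprecise, but it would address the right question.

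**The case against.** The strongest reply is that 12.5 already deals with most index-disease events. Ventilation, oxygen support and natural-history progression are kept out of SAE reporting, and the first limb of the AESI depends on SAE criteria. A reader might infer that worsening COVID-19 pneumonia in general counts as a serious-infection AESI. The documents do not support that: only the fatal case is clear, and the rest is ambiguous.

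A reader might also infer that the trial's main infection-safety comparison is partly its efficacy endpoint. No such comparison is designated. Safety is descriptive, and the overview AESI figure also includes liver injury, hypersensitivity, neutropenia and cytokine release. The figure affected is the infection class count. Even that assumes fatal COVID-19 is coded there, which the SAP does not state.

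Nor does the plan hide secondary infections outright. The preferred-term tables and listings show specific terms, sites are asked to look for the pathogen, and the DMC sees unblinded safety data. The Phase 2 statement in Section 4 cites sepsis and septic shock, not COVID-19 pneumonia, so it is not evidence of contamination.

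Finally, viral infection is within the listed risk, so removing the index infection from the AESI could narrow safety capture, and enrollment has closed.

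All of this stands and limits the point. It does not supply the missing number. One subject can appear in several preferred-term rows, so the rows cannot be added to give subjects affected. Terms such as pneumonia could be index or secondary disease. The 12.5 exceptions concern SAE reporting and do not settle the AESI question, so sites may differ.

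**Conclusion.** The point holds as a gap in definition and tabulation. Fatal COVID-19 pneumonia meets the serious-infection AESI as written; non-fatal progression is undecided because 12.2.1.3 and 12.5 are not aligned. The pooled infection count can therefore fall through efficacy alone and partly mask an excess of secondary infections.

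The size cannot be fixed from the documents. It rests on f and s, on independence, on a common f across arms, and on the drug working as planned. If sites apply the 12.5 exceptions so strictly that few index events are recorded as AESIs, the masking is near zero. If a quarter to a half are recorded, a true doubling from 8% to 16% shrinks to a ratio between 1.34 and 1.07. The working does not show that masking occurred, only that the planned tables could not rule it out. This is a cheap improvement to make before lock; it does not threaten the efficacy analysis.

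**What to change.** 1. **Keep AESI capture as it is.** Reconcile Protocol 12.2.1.3 with the exceptions in 12.5 by stating whether progression of the index disease counts as a serious-infection AESI. With enrollment closed, this cannot change how earlier events were reported, but it tells the analyst how to read them.
2. **Phase 3 SAP 5.8.1.** Add a by-arm table of subjects with at least one serious or opportunistic infection other than index COVID-19, with index COVID-19 terms in a separate row.
3. **Term list.** Fix the preferred terms for each row by blinded medical review before database lock.

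The cost is a clarifying sentence, one blinded term review and one table built from data already collected. The downside is that non-specific terms such as pneumonia or sepsis need a blinded judgement on whether they are index or secondary, and some will stay uncertain.
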